4.2 Scientific Rationale for Study Design

This is a global study designed to investigate the safety and efficacy of fixed dose tezepelumab (210 mg) administered SC starting at randomisation and then every 4 weeks (Q4W) for a total of 13 doses, on top of standardised INCS, in participants with severe bilateral NP who remain symptomatic despite standard of care therapy. To avoid bias the study will be randomised and double blinded. The population is composed of participants with ongoing chronic symptoms for at least 8 weeks prior to enrolment with moderate to severe participant reported nasal congestion, and a physician endoscopic diagnosis of bilateral NP (NPS of at least 5 out of a maximum of 8), despite documented treatment with SCS within the past 2 years and/or history of any NP surgical intervention. The disease severity at enrolment and history of failure with standard pharmacological treatment constitute an accepted indication for surgery or for a targeted biologic therapy such as tezepelumab, for participants who are not willing to or are contraindicated to have surgery.

CRSwNP is a heterogeneous disease ([Hull and Chandra 2017](#)). The eosinophilic (Type 2 high) endotype is most common in the United States, Europe, and Japan whilst non-eosinophilic endotype is more frequent in other Asian countries ([Lou H et al 2018](#), [Hull and Chandra 2017](#), [Fokkens et al 2020](#), [Shin SH et al 2014](#), [Chitsuthipakorn W et al 2018](#)). To ensure that endotypes are represented appropriately in all countries in this study capping will be used in China to ensure that approximately 80% of participants have an eosinophilic endotype

(defined by JESREC score of ≥ 11) ([Tokunaga T et al 2015](#)) to match the distribution predicted in the rest of the world.

The sample size (approximately 400 participants) is considered appropriate to demonstrate treatment effects with tezepelumab. The 52-week treatment duration is considered appropriate to capture maintenance effects in this chronic disease, assessment of endpoints of time to first SCS use and/or surgery (and the individual components), and proportion of participants with resolution/near complete resolution of nasal polyps as well as providing 1-year treatment safety data in the intended population. Approximately the first 200 randomised participants will have a 24-week follow-up period to evaluate durability of response and to provide off-treatment safety data.

Nasal polyp tissue will be obtained by biopsy in a subset of participants and in a limited number of sites globally. Histopathology of tissue inflammatory cells is commonly used globally as the most definitive method for defining participant endotype. The aim of the nasal biopsy is to characterise the inflammatory patterns of participants entering the sub-study as well as to explore the effect of tezepelumab treatment on nasal polyp inflammatory cells.

4.3 Justification for Dose

A 210 mg Q4W dosing regimen was selected for this Phase 3 study based on the similarity of the pathophysiology of CRSwNP and asthma and the efficacy, safety and exposure-response analysis from the Phase 2b Study CD-RI-MEDI9929-1146 (D5180C00001) in asthma.

Efficacy data from Study CD-RI-MEDI9929-1146 demonstrated that the 210 mg tezepelumab Q4W dose led to improved clinical efficacy compared to 70 mg Q4W, whereas the 280 mg Q2W dose did not further increase efficacy compared to 210 mg Q4W, and the safety profiles were similar across the 3 doses. Exposure-response modelling further confirmed the 210 mg Q4W dose is at the plateau of the exposure-response curves for the effect of tezepelumab on asthma exacerbation rate and FeNO. Given these results, the dose of 210 mg SC Q4W was confirmed in the tezepelumab Phase 3 programme for patients with severe asthma.

Given the similarity of the underlying inflammatory pathophysiology of asthma and nasal polyps and significant overlap in patient populations ([Fokkens et al 2020](#)), it is expected that the same dose of 210 mg Q4W SC would effectively target the inflammatory pathways relevant to both diseases and show efficacy in CRSwNP. This is supported by the post-hoc analysis of data from study CD-RI-MEDI9929-1146 in asthma patients with co-morbid nasal polyps (N= 18 in the placebo group and N= 23 in the 210 mg Q4W tezepelumab group). In these patients, treatment with tezepelumab resulted in marked reductions in blood eosinophil, IL-5, and IL-13 levels, all of which play a role in the pathogenesis of CRSwNP. Furthermore, there was similar efficacy with respect to asthma outcomes in patients with and without a history of nasal polyps, and to date there has been no change in the benefit/risk profile based on the completed studies. Based on the above rationale, the same tezepelumab dose as used in

the asthma Phase 3 studies, 210 mg Q4W SC is selected for this Phase 3 study in patients with CRSwNP.

4.4 End of Study Definition

A participant is considered to have completed the study if he/she has completed all phases of the study including the last scheduled procedure shown in the Schedule of Activities ([Table 1](#)).

The end of the study is defined as the date of the last scheduled procedure shown in the Schedule of Activities for the last participant in the study globally.

See Appendix [A 6](#) for guidelines for the dissemination of study results.

5 STUDY POPULATION

Prospective approval of protocol deviations to recruitment and enrolment criteria, also known as protocol waivers or exemptions, is not permitted.

Each participant should meet all the inclusion and none of the exclusion criteria for this study in order to be assigned/randomised to a study intervention. Under no circumstances can there be exceptions to this rule. Participants who do not meet the entry requirements are screen failures (see Section [5.4](#)).

In this protocol, “enrolled” participants are defined as those who sign informed consent. “Randomised” participants are defined as those who undergo randomisation and receive a randomisation number.

For procedures regarding withdrawal of incorrectly enrolled or randomised participants see Section [6.3](#).

5.1 Inclusion Criteria

Participants are eligible to be included in the study only if all the following criteria apply:

Age

1 Participant must be 18 years of age or older, at the time of signing the informed consent.

Type of Participant and Disease Characteristics

2 Participants with physician-diagnosed CRSwNP for at least 12 months prior to Visit 1 that have:

- Severity consistent with need for surgery as defined by total NPS ≥ 5 (at least 2 for each nostril) at screening, as determined by the central reader
- Nasal Congestion Score (NCS) ≥ 2 at Visit 1

- Ongoing documented NP symptoms for > 8 weeks prior to screening such as rhinorrhoea and/or reduction or loss of smell
- 3 SNOT-22 total score ≥ 30 at screening (Visit 1).
- 4 Any standard of care for treatment of CRSwNP provided the participant is stable on that treatment for at least 30 days prior to Visit 1.
- 5 Documented treatment of nasal polyp exacerbation with SCS for at least 3 consecutive days or one IM depo-injectable dose (or contraindications/intolerance to) within the past 12 months prior to Visit 1 but not within the last 3 months prior to Visit 1 and/or any history of NP surgery (or contraindications/intolerance to).

Weight

6 Body weight of ≥ 40 kg at Visit 1.

Sex

- 7 Male or female.
- 8 Female participants: Women not of childbearing potential are defined as women who are either permanently sterilised (hysterectomy, bilateral oophorectomy, or bilateral salpingectomy), or who are postmenopausal. Women will be considered postmenopausal if they have been amenorrhoeic for 12 months prior to the planned date of randomisation without an alternative medical cause. The following age-specific requirements apply:
 - (a) Women < 50 years old would be considered postmenopausal if they have been amenorrhoeic for 12 months or more following cessation of exogenous hormonal treatment and follicle-stimulating hormone levels in the postmenopausal range.
 - (b) Women ≥ 50 years old would be considered postmenopausal if they have been amenorrhoeic for 12 months or more following cessation of all exogenous hormonal treatment.
- 9 Female participants of childbearing potential must use one highly effective form of birth control. A highly effective method of contraception is defined as one that can achieve a failure rate of less than 1% per year when used consistently and correctly. Females of childbearing potential who are sexually active with a non-sterilised male partner must agree to use one highly effective method of birth control as defined below, from screening throughout the study and until at least 16 weeks after the final dose of IP. Contraceptive use by women should be consistent with local regulations regarding the methods of contraception for those participating in clinical studies. Cessation of contraception after this point should be discussed with a responsible physician. Periodic abstinence (calendar, symptothermal, post-ovulation methods), withdrawal (coitus interruptus), spermicides only, and lactational amenorrhoea method are not acceptable methods of contraception. Female condom and male condom should not be used together. All women of childbearing potential must have a negative serum pregnancy test results at Visit 1 and a negative urine pregnancy test at randomisation.

- Highly effective birth control methods include: true sexual abstinence, a vasectomised sexual partner, Implanon™, bilateral tubal occlusion, intrauterine device/levonorgestrel intrauterine system (IUD/IUS), Depo-Provera™ injections, oral contraceptive, and Evra Patch™, Xulane™, or NuvaRing™. Women of childbearing potential must agree to use one highly effective method of birth control, as defined above, from screening throughout the study and until at least 16 weeks after the final dose of IP.

Informed Consent

- 10 Capable of giving signed informed consent as described in [Appendix A](#) which includes compliance with the requirements and restrictions listed in the informed consent form (ICF) and in this protocol.
- 11 Provision of signed and dated, written informed consent form (ICF) prior to any mandatory study specific procedures, sampling, and analyses and according to international guidelines and/or applicable EU guidelines.
- 12 Provision of signed and dated written optional Genetic Research Information informed consent prior to collection of samples for optional genetic research that supports Genomic Initiative (if applicable).
- 13 Provision of signed and dated written addendum to optional informed consent form for nasal biopsy sub-study prior to collection of nasal biopsy samples (if applicable).

Participant must meet the following criteria at the randomisation visit (Visit 3):

- 14 Confirmed central reading total NPS ≥ 5 (at least 2 for each nostril) at Visit 2.
- 15 Inclusion Criterion 15 replaced with Criterion 15a in a prior version of the Clinical Study Protocol
- 15a) At randomisation visit (Visit 3), a bi-weekly mean NCS ≥ 2 (baseline bi-weekly score collected from study Day -13 to study Day 0).
- 16 SNOT-22 score ≥ 30 at randomisation (Visit 3).
- 17 At least 8 days of evaluable daily diary data in the 14-day period prior to randomisation (baseline bi-weekly mean score collected from study Day -13 to study Day 0).
- 18 Minimum compliance with the daily eDiary during the screening and run-in periods (having a minimum of 70% fully compliant days from Visit 1 to the day of randomisation at Visit 3).
- 19 Minimum compliance with background INCS as captured in the eDiary during the screening and run-in periods (having a minimum of 70% fully compliant days from Visit 1 to the day of randomisation at Visit 3).
 - Days of missing eDiary data treated as non-compliant for this criterion.

5.2 Exclusion Criteria

Participants are excluded from the study if any of the following criteria apply:

Medical Conditions

- 1 Any clinically important comorbidities other than asthma (eg, active lung infection, bronchiectasis, pulmonary fibrosis, cystic fibrosis, primary ciliary dyskinesia, allergic bronchopulmonary mycosis, hypereosinophilic syndromes, etc) that could confound interpretation of clinical efficacy results.
- 2 Exclusion criterion number 2 was removed and merged with Exclusion number 5.
- 3 Any disorder, including but not limited to cardiovascular, gastrointestinal, hepatic, renal, neurological, musculoskeletal, infectious, endocrine, metabolic, haematological, psychiatric, or major physical impairment that is not stable in the opinion of the Investigator or AstraZeneca and could:
 - (a) Affect the safety of the participant throughout the study;
 - (b) Influence the findings of the studies or their interpretations;
 - (c) Impede the participant's ability to complete the entire duration of study.
- 4 Sinus surgery within 6 months of screening visit OR any sinus surgery in the past which changed the lateral wall of the nose making NPS evaluation impossible.
- 5 Participants with conditions or concomitant disease that makes them non-evaluable for the primary efficacy endpoint such as:
 - antrochoanal polyps;
 - nasal septal deviation that occludes at least one nostril;
 - acute sinusitis, nasal infection, asthma exacerbation or upper respiratory infection at screening or in the 2 weeks before screening; or Churg-Strauss syndrome (also known as known as Eosinophilic granulomatosis with polyangiitis (EGPA)), Young's syndrome or Kartagener's syndrome.
- 6 A history of known immunodeficiency disorder, including a positive human immunodeficiency virus (HIV) test at Visit 1, or the participant taking antiretroviral medications as determined by medical history and/or participants verbal report.
- 7 Positive hepatitis B surface antigen, or hepatitis C virus antibody serology at screening, or a positive medical history for hepatitis B or C. Participants with a history of hepatitis B vaccination without a history of hepatitis B and participants with hepatitis C who have been cured are allowed to participate.
- 8 Known history of chronic drug or alcohol abuse within 12 months prior to Visit 1, based on Investigator's assessment.
- 9 Primary Ciliary Dyskinesia (PCD).
- 10 Uncontrolled epistaxis within 2 months of Visit 1.

- 11 Known or suspected history of immunosuppression, immune dysfunction or immune dysregulation which may include but is not limited to conditions such as: Guillain-Barré syndrome, invasive opportunistic infections (eg, histoplasmosis, listeriosis, coccidioidomycosis, pneumocystosis, aspergillosis), or unusually frequent, recurrent, or prolonged infections, per Investigator judgement.
- 12 History of cancer:
 - (a) Participants who have had basal cell carcinoma or localised squamous cell carcinoma of the skin or in situ carcinoma of the cervix are eligible to participate in the study provided that the participant is in remission and curative therapy was completed at least 12 months prior to Visit 1.
 - (b) Participants who have had other malignancies are eligible provided that curative therapy was completed at least 5 years prior to Visit 1.
- 13 A helminth parasitic infection diagnosed within 24 weeks prior to the date of informed consent that has not been treated with or has failed to respond to standard of care therapy.
- 14 Tuberculosis requiring treatment within the 12 months prior to Visit 1.
- 15 Major surgery within 8 weeks prior to Visit 1 or planned nasal polyp surgery during the conduct of the study.
- 16 Infection requiring systemic antibiotics within 14 days prior to Visit 1.
- 17 Positive SARS-CoV-2 nasopharyngeal swab test (or COVID-19 rapid test) or COVID-19 entry screening questionnaire during the screening visit.
 - Evaluation will be based on local standard of care as determined by current local guidelines.

Prior/Concomitant Therapy

- 18 Receipt of any marketed or investigational biologic (monoclonal or polyclonal antibody) within 4 months or 5 half-lives prior to the date informed consent is obtained, whichever is longer, and during the study period. This also applies to participants who previously participated in clinical studies and were treated with monoclonal antibodies (eg, mepolizumab, reslizumab, dupilumab, benralizumab, omalizumab). Note that this restriction does not apply to participants, who are confirmed to have only received treatment with placebo.
- 19 Initiation of new allergen immunotherapy is not allowed unless participant is already on stable therapy started 30 days prior to Visit 1 with no change during the treatment period.
- 20 Regular use of decongestants (topical or systemic) at enrolment is not allowed unless used for endoscopic procedure.
- 21 Use of immunosuppressive medication (including but not limited to methotrexate, troleandomycin, cyclosporine, azathioprine, mycophenolate, tacrolimus, gold, penicillamine, sulfasalazine, hydroxychloroquine, systemic corticosteroids or any

experimental anti-inflammatory therapy) within 3 months prior to Visit 1 and during the study period.

- Systemic corticosteroid use is defined as treatment with a burst of systemic corticosteroids for at least 3 consecutive days or a single IM depo-injectable dose of corticosteroids (considered equivalent to a 3-day burst of systemic corticosteroids)

22 Use of corticosteroid-eluting intranasal stents within 6 months prior to Visit 1 and during the study period.

23 Receipt of immunoglobulin or blood products within 30 days prior to Visit 1.

24 Receipt of any non-biologic investigational drug within 30 days or 5 half-lives whichever is longer prior to the date of informed consent.

25 Known history of allergy or reaction to any component of the IP formulation.

26 History of anaphylaxis or documented immune complex disease (Type III hypersensitivity reactions) following any biologic therapy.

27 Recent Aspirin desensitisation within 6 months of enrolment.

28 Receipt of live attenuated vaccines 30 days prior to the date of randomisation.

- Receipt of inactive/killed vaccinations (eg, inactive influenza) is allowed provided they are not administered within 5 days before/after any tezepelumab administration.

Diagnostic Assessments

29 Any clinically significant abnormal findings in physical examination, vital signs, haematology, clinical chemistry, or urinalysis during screening/run-in period, which in the opinion of the Investigator, may put the participant at risk because of his/her participation in the study, or may influence the results of the study, or the participant's ability to complete entire duration of the study.

30 Any clinically significant cardiac disease or any electrocardiogram (ECG) abnormality obtained during the screening/run-in period, which in the opinion of the investigator, may put the participant at risk or interfere with study assessments.

31 Evidence of active liver disease, including jaundice or aspartate transaminase (AST), alanine transaminase (ALT), or alkaline phosphatase (ALP) > 2 times the upper limit of normal (ULN) at Visit 1.

Other Exclusions

32 Involvement in the planning and/or conduct of the study (applies to both AstraZeneca staff and/or staff at the study site).

33 Judgement by the investigator that the participant should not participate in the study if the participant is unlikely to comply with study procedures, restrictions, and requirements.

34 Previous randomisation in the present study.

35 For women only - currently pregnant (confirmed with positive pregnancy test), breastfeeding or lactating women.

- A serum pregnancy test will be done for women of childbearing potential at screening Visit 1 and a urine pregnancy test must be performed for women of childbearing potential at each treatment visit prior to IP administration. A positive urine test result must be confirmed with a serum pregnancy test. If serum test is positive, the participant should be excluded.

36 Chronic alcohol or drug abuse within 12 months prior to Visit 1 and throughout the conduct of the study.

- **For participants with co-morbid asthma:** Current smokers or participants with smoking history \geq 10 pack-years at Visit 1 will not be allowed to randomise in the study. Former smokers with a smoking history of $<$ 10 pack-years must have stopped for at least 6 months to be eligible. Smoking is not allowed throughout the course of the study; this includes e-cigarettes.

37 Receipt of COVID-19 vaccine (regardless of vaccine delivery platform) 28 days prior to date of IP administration at V3 (randomisation visit).

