2.3.1 Risk Assessment

Table 2 Risk Assessment

Important potential risks	Summary of data/rationale for risk	Mitigation strategy
Study intervention		
Serious infections are defined as infections fulfilling criteria for regulatory reporting	
The mechanism of action of tezepelumab suggests potential inhibitory effects on immune responses mediated by Th2 cells, leading to the possibility of diminution of the host's protective response to infection. Although there is a theoretical risk of serious infections with tezepelumab treatment, there is no data to support this potential risk. There is also no evidence for causal relationship with tezepelumab.
	
Vulnerable participants will be excluded based on eligibility criteria, and randomised participants will be monitored by safety blood work throughout the study; and through standard AE/SAE reporting.
 
Participants will be excluded if they received systemic immunosuppressive or immunomodulating drugs within the last 12 weeks or 5 half-lives (whichever is longer) prior to Visit 1; or if they have a history of a known immunodeficiency disorder; or have a history of clinically significant infection requiring treatment with systemic antibiotics or antiviral medications finalised < 2 weeks before Visit 1 or during the run-in period or at randomisation; or who have evidence of active coronavirus disease 2019 (COVID-19) infection during the run-in period or optimisation phase; or have had tuberculosis requiring treatment within the 12 months prior to Visit 1.
 
Serious infections are an AESI and participants who develop serious infection will be followed up closely throughout study.

Malignancies	
Given the potential theoretical risk, the long-term treatment intended for a chronic disease and the nature of malignancy development, malignancy is included as an important potential risk.
 
There is no evidence to suggest increase in malignancies in the data to-date in either nonclinical or clinical studies. No causal relationship with tezepelumab could be established for cases reported.
	
Participants with current malignancy or whose curative therapy was completed recently will be excluded from participation based on eligibility criteria. All participants will be closely followed during the study for any adverse events/serious adverse events, including malignancies that are considered AESI.

Table 2 Risk Assessment

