Intranasal Medication including intranasal corticosteroids drops	Only study provided MFNS or equivalent INCS is allowed.
Any immunosuppressive treatment including but not limited to: methotrexate, cyclosporine, mycophenolate, tacrolimus, gold, penicillamine, sulfasalazine, hydroxychloroquine, azathioprine, cyclophosphamide	Not allowed within 3 months prior to V1; during the study period and 3 months or 5 half-lives (whichever is longer) after last dose of the IP.
Aspirin desensitisation	Use of aspirin as a desensitisation regimen for the management of aspirin exacerbated respiratory disease (AERD) is not allowed; all other uses of aspirin are allowed for any other medical conditions.
Any marketed or investigational biologic (monoclonal or polyclonal antibody)	Not allowed within 4 months or 5 half-lives (whichever is longer) prior to V1; during screening/run-in and throughout the IP treatment, and 4 months or 5 half-lives (whichever is longer) after the last dose of IP.
Other investigational product	Not allowed within 30 days or 5 half-lives (whichever is longer) prior V1, during screening/run-in and throughout the IP treatment and preferably 4 weeks after the last dose of IP.
Live attenuated vaccines	Not allowed within 30 days prior to randomisation; during the study period, and 16 weeks or 5 half-lives (whichever is longer) after the last dose of the IP.
Blood products or immunoglobulin therapy	Not allowed 30 days prior to Visit 1, during screening/run-in and throughout the IP treatment and preferably 4 weeks after the last dose of IP.
Herbal remedies for the treatment of CRSwNP	Not allowed 30 days prior to Visit 1, during screening/run-in and throughout the IP treatment and preferably 4 weeks after the last dose of IP.

The Medical Monitor should be contacted if there are any questions regarding concomitant or

prior therapy.

Participants must abstain from taking prescription or non-prescription drugs for nasal polyps (including vitamins and dietary or herbal supplements) within 7 days (or 14 days if the drug is a potential enzyme inducer) or 5 half-lives (whichever is longer) before the start of study intervention until completion of the follow-up visit, unless, in the opinion of the investigator and sponsor, the medication will not interfere with the study.

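### Table 2 promises a washout of 12 weeks or 5 half-lives for immunosuppressants, but exclusion 21 and Table 6 apply a flat 3 months, so long-half-life drugs fall outside the stated safeguard

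*Protocol*

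**What the plan says.** The protocol gives two washout rules for the same class of drug.

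- **Section 2.3.1, Table 2**, the mitigation for serious infections, says vulnerable participants are kept out through the eligibility criteria. It then names those who took "systemic immunosuppressive or immunomodulating drugs within the last 12 weeks or 5 half-lives (whichever is longer) prior to Visit 1".
- **Section 5.2, exclusion 21**, lists immunosuppressants in an open-ended way and bars them, together with any "experimental anti-inflammatory therapy) within 3 months prior to Visit 1 and during the study period". It has no half-life term.
- **Section 6.4, Table 6**, the immunosuppressant row, reads "Not allowed within 3 months prior to V1; during the study period". A 5-half-life alternative appears in that row, but only for the period after the last dose of investigational product.

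Section 5 settles which rule governs entry: "Each participant should meet all the inclusion and none of the exclusion criteria for this study in order to be assigned/randomised".

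Neighbouring rules do carry a half-life term:

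- Exclusion 18 bars biologics "within 4 months or 5 half-lives prior to the date informed consent is obtained, whichever is longer".
- Exclusion 24 covers "Receipt of any non-biologic investigational drug within 30 days or 5 half-lives whichever is longer prior to the date of informed consent".
- Section 6.4 also tells participants to "abstain from taking prescription or non-prescription drugs for nasal polyps (including vitamins and dietary or herbal supplements) within 7 days" of first dose, extended to 5 half-lives for longer-acting drugs. That rule is limited to drugs taken for nasal polyps, counts back from first dose and can be waived where investigator and sponsor judge that the drug does not matter to the study.

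**The concern.** Table 2 presents the half-life washout as a safeguard that the eligibility criteria already contain. They do not contain it. A participant who stopped a long-half-life immunosuppressant a little over 3 months before Visit 1 satisfies exclusion 21, yet Table 2 tells a reader of the benefit/risk section that this person is excluded.

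What is at stake is whether one stated mitigation for an important potential risk matches what sites do. Allocation is 1:1, so about half of any such participants would receive tezepelumab. The documents do not link residual drug to infection risk, so no size of harm can be given. Sample size, power, type I error and the treatment comparison are not in question.

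**Working it through.** **Which drugs are left.** Biologics fall under exclusion 18 and investigational non-biologics under exclusion 24, both with 5 half-lives. That leaves marketed non-biologic immunosuppressants. Those taken for nasal polyps meet the waivable Section 6.4 rule; those taken for other conditions meet no half-life rule.

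**Inputs**

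- Table 2: the longer of 84 days (12 weeks) and 5t before Visit 1, where t is the half-life in days.
- Exclusion 21 and Table 6: 3 months before Visit 1, taken as 91.3 days (calendar range 89 to 92).
- Section 6.4, nasal polyp drugs: 5t before first dose.
- Visit 1 to first dose: 35 days, from the 5-week screening/run-in period in Section 1.1.
- Half-lives: the documents give none, so 30, 40 and 60 days are assumptions. Residual drug assumes simple exponential decay.

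**Where the rules part**

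- At Visit 1: 91.3/5 = 18.3 days (89/5 = 17.8 to 92/5 = 18.4). Up to this half-life the flat 3 months is equal or stricter, since 91.3 days exceeds both 84 days and 5t.
- At first dose: (91.3 + 35)/5 = 25.3 days. Between 18.3 and 25.3 days the rules differ at Visit 1, but 5 half-lives have passed by first dose. Above 25.3 days the gap is still open when dosing starts.

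**Days off drug required before Visit 1**

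| Half-life t (assumed) | Table 2: max(84, 5t) | Exclusion 21 alone | With Section 6.4: max(91.3, 5t − 35) |
|---|---|---|---|
| 30 days | 150 | 91.3 | 115 |
| 40 days | 200 | 91.3 | 165 |
| 60 days | 300 | 91.3 | 265 |

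**Drug remaining at first dose**, 2^(−(days before Visit 1 + 35)/t)

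| Half-life t (assumed) | Table 2 | Exclusion 21 alone | With Section 6.4 |
|---|---|---|---|
| 30 days | 2^(−185/30) = 1.4% | 2^(−126.3/30) = 5.4% | 2^(−5) = 3.1% |
| 40 days | 2^(−235/40) = 1.7% | 2^(−126.3/40) = 11.2% | 3.1% |
| 60 days | 2^(−335/60) = 2.1% | 2^(−126.3/60) = 23.2% | 3.1% |

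The practical gap is therefore drugs taken for other conditions with half-lives above about 25 days, plus nasal polyp drugs of that kind where Section 6.4 is waived.

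**The case against.** The strongest reply is that this is an editorial slip with no demonstrated consequence. No document gives a half-life for any immunosuppressant, so no affected drug or participant is shown, and every residual percentage rests on an assumed value. That is correct, and it is why the point is minor.

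A second argument is that sites have one clear rule, because Section 5 governs and Table 6 agrees with exclusion 21 before Visit 1. The fault would then lie in loose wording in Table 2, which also refers to an optimisation phase not described elsewhere and gives 6 months for helminth infection where exclusion 13 gives 24 weeks. This may well be the origin of the mismatch. It affects which text to correct, not whether the two agree. Against it, the sponsor uses the half-life wording in exclusions 18 and 24 and in the post-dose part of the same Table 6 row, so an omission is also plausible.

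A third argument is that other criteria act as backstops. Exclusion 11 covers a known or suspected history of immunosuppression, exclusion 3 covers unstable disorders that could affect safety, and exclusion 29 covers clinically significant findings at screening. An investigator could act on treatment history alone under exclusion 11. These criteria are real protection, but they depend largely on judgement and none sets a washout.

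Finally, Table 2 lists several other infection safeguards, including exclusions for immunodeficiency, recent infection and tuberculosis, safety bloods and close follow-up of serious infections. Those stand; only one tail of one window is affected.

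**Conclusion.** The inconsistency is real: as written, the entry rules admit people whom the protocol's own serious-infection mitigation says are excluded. It applies to marketed non-biologic immunosuppressants with half-lives above about 18 days at Visit 1. It matters in practice above about 25 days, for drugs taken for other conditions or where the Section 6.4 rule is waived.

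The thresholds rest on 3 months being about 91 days and on a nominal 35-day run-in; a longer screening period would raise the second threshold. The residual percentages rest on assumed half-lives and exponential decay. The number of participants cannot be estimated from the documents but is likely to be small. This is a minor correction with no claimed effect on the efficacy analysis.

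**What to change.** If enrolment is open and the Table 2 rule is intended, add a 5-half-life alternative to the pre-Visit 1 window in exclusion 21 and in the immunosuppressant row of Table 6, with the longer period applying. This is one clause in each place. It changes an entry rule, so it needs an amendment with IRB/IEC and regulatory approval (Appendix A 1), and it may cause a few later entries or screen failures.

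If the flat 3 months is intended, or recruitment has closed, correct Table 2 so that it no longer claims a half-life-based exclusion. SAP edition 4 is dated 21 August 2024 and the SAP is to be final before the primary database lock, which suggests, without proving, that this is now the realistic route. It is one clause and leaves eligibility unchanged. It may still carry an approval step, since the v5.0 amendment log in Appendix J classed an earlier change to Table 2 as substantial.

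Neither route needs new data collection, because medication use is already recorded under Section 6.4.
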